## Statistical Analysis of Subjective Effect Parameters

A linear mixed effects model for analysis of variance/covariance (Proc Mixed) will be performed on  $E_{max\_urge}(\text{controlled})$  and  $E_{max\_plst}(\text{controlled})$ . The model will include  $E_{max}$  as the response variable, sequence, study product, and period as fixed model effects, baseline score as a covariate, and subject nested-within sequence as a random effect. Sequence will be tested using subject nested-within-sequence as the error term. Least square mean (LSM) and 95% confidence interval (CI) for each study product group will be provided. Comparisons will be made for Product A vs. B, A vs. C and B vs. C. The comparison between Product A and Product C will be used as a comparison for internal validity. The LSM difference, p-value and 95% CI of the difference will be provided.

The SAS code for the statistical modeling is:

```
Proc MIXED data=test;
  class subject sequence period product;
  model Emax = sequence period product baseline / ddfm=KR;
  random subject (sequence) / type=UN;
  estimate "Product A vs Product B" product 1 0 -1 /cl alpha=0.05;
  estimate "Product A vs Product C" product 1 0 -1 /cl alpha=0.05;
  estimate "Product B vs Product C" product 0 1 -1 /cl alpha=0.05;
  lsmeans product/cl alpha=0.05;
run;
```

The same model will be used for  $E_{max\_urge}(\text{uncontrolled})$  and  $E_{max\_plst}(\text{uncontrolled})$ , and all  $E_{max}$  of other questions in the Tobacco/Nicotine Withdrawal Questionnaire and Direct Effects of Product Questionnaire for the controlled and uncontrolled product uses in Part B. Baseline (pre-use) score will be included as a covariate for all pharmacodynamics measures for which a pre-use score is collected.

The analysis on  $E_{max\_urge(\text{controlled})}$  and  $E_{max\_plist(\text{controlled})}$  will be based on the pharmacodynamic and the completer populations separately.

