#### Statistical Analysis of PK Parameters

A linear mixed model for analysis of variance (Proc Mixed) will be performed on the baseline-adjusted log transformed nicotine PK parameters in Part B ( $C_{\text{max}}(\text{controlled})$ ,  $C_{\text{max}}(\text{uncontrolled})$ ,  $AUC_{(\text{controlled})}$  and  $AUC_{(\text{controlled})}$ ). The model will include sequence, study product, and period as fixed effects and subject nested-within sequence as a random effect. Sequence will be tested using subject nested-within sequence as the error term. From each model, the geometric LSM and 95% confidence intervals will be calculated for each study product. Separate analyses will be performed on the parameters calculated for the Controlled and Uncontrolled Use sessions. Geometric mean ratios for each pair comparison, 95% confidence interval and p value will be provided.

The SAS codes for the model will be as follows:

```
Proc MIXED data=test;
  class subject sequence period product;
  model log(Cmax0_180) = sequence period product / ddfm=KR;
  random subject (sequence) / type=UN;
  estimate "Product A vs Product B" product 1 -1 0 /cl alpha=0.05;
  estimate "Product A vs Product C" product 1 0 -1 /cl alpha=0.05;
  estimate "Product B vs Product C" product 0 1 -1 /cl alpha=0.05;
  lsmeans product/cl alpha=0.05;
run;
```

The Hodges-Lehmann's method will be used to estimate the median differences and the 95% confidence interval of  $T_{\text{max}}$  and  $T_{1/2}$  between the products for controlled and uncontrolled use.

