**Similar table(s) :**

T14.2.3.3.1.2	Statistical Analysis of Subjective Effect Parameters for Tobacco/Nicotine Withdrawal - Product A vs Product C
T14.2.3.3.1.3	Statistical Analysis of Subjective Effect Parameters for Tobacco/Nicotine Withdrawal - Product B vs Product C
T14.2.3.3.2.1	Statistical Analysis of Subjective Effect Parameters for Direct Effect of Product Questionnaire - Product A vs Product B
T14.2.3.3.2.2	Statistical Analysis of Subjective Effect Parameters for Direct Effect of Product Questionnaire - Product A vs Product C
T14.2.3.3.2.3	Statistical Analysis of Subjective Effect Parameters for Direct Effect of Product Questionnaire - Product B vs Product C

Table 14.2.3.3.1.4  
Statistical Analysis of Subjective Effect Parameters for Tobacco/Nicotine Withdrawal  
(Completer Population)

Subjective Effect Parameter	Product Use Session	Comparison	Lsmeans [1]			95% Confidence Interval		
			Product	vs Product	Difference (SD)	P value of Product Effect	Lower Bound	Upper Bound
Emax_urge	Controlled Use	Product A vs Product D	xxxxxx	xxxxxx	XXXXXX (xx.x)	xxx	xxx	xxx
		Product B vs Product D	xxxxxx	xxxxxx	XXXXXX (xx.x)	xxx	xxx	xxx
		Product C vs Product D	xxxxxx	xxxxxx	XXXXXX (xx.x)	xxx	xxx	xxx
		Etc.						
Ad libitum	Use	Product A vs Product D	xxxxxx	xxxxxx	XXXXXX (xx.x)	xxx	xxx	xxx
		Etc.						

Note(s): The Analysis of Variance (ANOVA) model included the Emax as the response variable, sequence, study product, and period as fixed model effects, baseline score as a covariate and subject nested-within sequence as a random effect.

Date: VERSION - YYYY-MM-DD

Data Source: XXXX

Program Source: XXXXX.sas

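### Run as written, the SAP's primary-model SAS code reports VLN versus gum under the label VLN versus own-brand, and gives no inference for VLN versus own-brand

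*SAP*

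**What the plan says.** The text of SAP Section 9 (Statistical Analysis of Subjective Effect Parameters) states the intended contrasts: "Comparisons will be made for Product A vs. B, A vs. C and B vs. C". Each is to have an LSM difference, a p-value and a 95% CI, and A versus C is given the role of an internal-validity check.

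The code that follows contains these statements:

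- Class variables: "class subject sequence period product"
- Labelled A versus B: "estimate 'Product A vs Product B' product 1 0 -1 /cl alpha=0.05"
- Labelled A versus C: "estimate 'Product A vs Product C' product 1 0 -1 /cl alpha=0.05"
- Labelled B versus C: "estimate 'Product B vs Product C' product 0 1 -1 /cl alpha=0.05"
- Least-squares means: "lsmeans product/cl alpha=0.05"

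The PK model in the same section codes the A versus B contrast differently: "estimate 'Product A vs Product B' product 1 -1 0 /cl alpha=0.05".

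In SAP Appendix C, the shell for Table 14.2.3.3.1.1 has a column for the A minus B difference. The Completer Population shell (Table 14.2.3.3.1.4) has rows such as "Product A vs Product D", although the study has only Products A, B and C. SAP Section 12 declares no departures from the protocol's analyses.

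**The concern.** Two differently labelled contrasts share one coefficient vector, so at least one of them is wrong. PROC MIXED treats the label as free text and computes from the coefficients. The mislabelled line is the one for VLN against own-brand.

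That comparison carries the study's purpose. The primary objective names own-brand and gum together without ranking them. However, the Study Rationale (Protocol 5.2) looks for evidence of lower abuse liability relative to own-brand, and the SAP assigns VLN against gum to internal validity. Executed literally, the code would print the internal-validity contrast twice, once under the own-brand label, for both primary endpoints and for every secondary Emax endpoint that uses the model.

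**Working it through.** **1. What the coefficients estimate.** The CLASS statement has no ORDER= option, so levels coded A, B, C sort in that order. Writing the product effects as A, B and C:

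| Label | Coefficients | Quantity returned |
|---|---|---|
| A vs B (PD code) | 1, 0, -1 | A - C |
| A vs C (PD code) | 1, 0, -1 | A - C |
| B vs C (PD code) | 0, 1, -1 | B - C |
| A vs B (PK code) | 1, -1, 0 | A - B |

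**2. Could another level order rescue it?** No. All six orderings were checked. Because two labels share one vector, at least one is wrong under each. Only the order A, B, C makes the A versus C and B versus C lines both correct, and the PK code assumes the same order.

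**3. Is A - B available elsewhere in the output?** LSMEANS has CL but not DIFF, so it prints single-product means only. The point difference can be found by subtraction, either from the two LSMs or as (A - C) - (B - C). Its variance is Var(A - C) + Var(B - C) - 2 Cov(A - C, B - C), and the code does not print the covariance. The promised CI and p-value are therefore missing.

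**4. Size of the error.** Reported minus intended = (A - C) - (A - B) = B - C. SAP Section 4 (Sample Size Determination) assumes B - C = 15.85 for urge and 35.21 for pleasant. These are the errors in the rows labelled A versus B under the plan's own assumptions.

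**5. The plan's sample size, as a check on those inputs.** Reading the SD as per-product or within-subject, the variance of a difference is 2·SD²/n.

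- Urge at n = 54: 15.85 / (28.44 × √(2/54)) = 2.896. Normal-approximation power is Φ(2.896 - 1.960) = 0.825.
- Pleasant at n = 16: 35.21 / (31.82 × √(2/16)) = 3.130. Power is Φ(3.130 - 1.960) = 0.879.

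Both agree with the plan's claim of more than 80%. With noncentral-t versions, power is 0.81 to 0.82 for urge and 0.83 to 0.86 for pleasant. The calculation concerns B versus C, which is coded correctly, so 54 is unaffected.

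**6. Effect on the urge result.** The documents give no expected VLN effect, so VLN's position between gum and own-brand was varied as an assumption. The simulation used the three-sequence crossover with n = 54, B - C = 15.85, residual SD 28.44, an assumed between-subject SD of 20, complete data and no baseline covariate, with 300 runs per scenario. The Monte Carlo error is about √(0.82 × 0.18 / 300) = 2 percentage points at 82%.

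| VLN position | Row labelled A vs B, as coded: mean (significant) | Correct A - B: mean (significant) |
|---|---|---|
| Same as gum | -0.45 (4%) | -15.89 (82%) |
| One quarter of the way to own-brand | +3.81 (12%) | -12.07 (55%) |
| Midway | +8.08 (28%) | -8.03 (31%) |
| Three quarters | +12.07 (58%) | -3.87 (9%) |
| Same as own-brand | +15.66 (82%) | +0.38 (4%) |

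Emax_urge is a reduction in urge, so a negative A - B means that VLN relieves urge less than own-brand. At one end of the range the code hides a real difference. In between it reverses the sign. At the other end it shows VLN as superior when the two are equal.

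**7. Reach.** The withdrawal questionnaire has 5 items and the direct-effects questionnaire has 8, each in two sessions: (5 + 8) × 2 = 26 analyses. The Completer runs of the two primary endpoints use the same model and are additional.

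**The case against.** The strongest reply is that this is a coding slip and not a design flaw. The prose, the protocol and the table shells all state A versus B correctly, so the estimand is not in doubt, and the harm arises only if the code is run verbatim. That is true.

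The error should also be easy to notice. The A versus B table prints both LSMs beside their difference, and the row would not subtract. The A versus B and A versus C tables would show identical differences, CIs and p-values throughout. SAP Section 13 requires program validation. These safeguards make publication of a wrong result less likely, but they do not correct the specification. The SAP presents this block as the code for the model, the error survives in Final 2.0, and validation against that code would reproduce it.

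It is also fair that the A - B point estimate is recoverable. With complete balanced data and no covariate, all pairwise standard errors would be equal and an interval could be inferred. The coded model includes a baseline covariate and complete data are not guaranteed, so the plan cannot rely on that.

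The Product D rows are a separate display fault. They do not alter the model, but they mean that the Completer tables as laid out offer no backstop.

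**Conclusion.** The concern holds. The primary-model code contradicts the SAP's own text, shells and PK code. If executed as written, it reports VLN versus gum as VLN versus own-brand for both primary endpoints, and gives no CI or p-value for the intended comparison.

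The identity that the error equals B - C is exact. Its size, 15.85 points (urge) and 35.21 points (pleasant), rests on the plan's assumed differences between own-brand and gum. The rejection rates also depend on the simulation settings and on VLN's unknown position, so they illustrate a range and do not predict the result.

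The PK analyses and the sample size are unaffected. This must be corrected before the analysis is run. SAP Section 6 classes analyses performed after database lock as post hoc and exploratory, and a later correction could invite dispute over the status of the main comparison.

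**What to change.** 1. In SAP Section 9, change the coefficients of the first ESTIMATE statement in the pharmacodynamic code to product 1 -1 0, as in the PK code.
2. Add DIFF to the LSMEANS statement, so that all pairwise differences are printed independently of hand-entered coefficients, and confirm that the product variable sorts A, B, C.
3. In Appendix C, replace the Product D rows in the Completer shell for Table 14.2.3.3.1.4 with A versus B, A versus C and B versus C. Table 14.2.3.3.2.4 is specified as similar to it and needs the same correction.

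The cost is one coefficient vector, one option and one shell (used for two tables) in a SAP amendment. Data collection, sample size and the intended comparisons do not change.

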7.1.2.3. Part B (Day 4 to 6)

Upon completion of Part A, subjects will be randomized to one of three product sequence groups in Part B, which will consist of 3 study days (Days 4 to 6), with one product per day. Each study

day will consist of: 1) Controlled Product Use Session (10 puffs from their own-brand cigarette or VLN cigarette [maximum 3 ± 2 seconds per puff] at approximately 30 ± 5 -second interpuff intervals^a, or chew the nicotine polacrilex gum using the “chew and park” method for 10 minutes); and 2) Uncontrolled Product Use Session (use of one unit of a product ad libitum for 10 minutes). The Controlled Product Use Session and Uncontrolled Product Use Session will be separated by approximately 6 hours. During Part B, pharmacodynamic measures, PK samples, and product use behavior (Uncontrolled Product Use Session only) will be collected at various time points each day (See [Table 1](#)).

Safety assessments, including AEs, physical examinations, vital signs (respiratory rate, pulse rate, blood pressure, and oral temperature), electrocardiogram (ECG), clinical laboratory tests (clinical chemistry, hematology, urinalysis, and serology), urine drug screen (UDS), and alcohol test will be collected at designated time points throughout the study.

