^g Spontaneous AE reporting is continuous throughout the study, beginning with the time the subject gives informed consent; however, at regular intervals, AE checks will be performed using a non-leading question.

^h Day 1 only

ⁱ Day 4 only

^j Trial of 4 mg nicotine polacrilex gum for 10 minutes

^k Product use under ad libitum condition for 4 hours on each day

^l First product under controlled use condition manner (10 puffs [maximum 3 ± 2 seconds per puff] with approximately 30-second inter-puff-intervals for cigarettes and 10 minutes “chew and park” for nicotine polacrilex gum) and second product under uncontrolled use condition for approximately 10 minutes (ad libitum) with approximately 6 hours in between 1st and 2nd use sessions

^m Blood samples collected at same time points following the start of the 1st and 2nd product use sessions. Pre-product use samples should be collected within approximately 5 minutes prior to the start of product use, all other time points should be taken within ± 1 minute for the first 30 minutes and ± 5 minutes from the nominal time for all other time points (except when coinciding with PD testing). Actual time of blood draw will be recorded.

ⁿ Additional PD training sessions may be performed throughout the study, as necessary.

^o Administered at same time points following the start of the 1st and 2nd product use sessions

	Screening	Check-in	Part A	Part B										End of Study/ET	
Day:	-28 to -2	-1	1 to 3	4 to 6 (Daily controlled use and uncontrolled use sessions)										6	
Assessment				Assessment timepoints (minutes ^a)											
Direct Effects of Product Questionnaire ^b				pre		5			15		30		60	90	
Use the product again VAS			X ^b										90 ^b		
Amount of product used			X ^c	< ^d	-	-	-	>							
Tobacco cessation information														X	
Admission		X													
Discharge														X	

NOTE: Pre-use assessments (not including PK) may be conducted up to 60 minutes prior to product use. When assessments coincide at any given timepoint during a product use session, the order of assessments should be pharmacodynamics assessments followed by PK. The pharmacodynamic assessments should be conducted at the nominal timepoint (± 2 minutes up to 30 minutes postdose and ± 5 minutes postdose thereafter). AE=adverse event; BMI=body mass index; ECG=electrocardiogram; ET=early termination; FSH=follicle stimulating hormone; HIV=human immunodeficiency virus; pre=pre-use

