9.4.2. Part B (Days 4 to 6)

On each of the 3 days, subjects will use only one of the 3 study products according to their randomization sequences. No other use of tobacco- or nicotine-containing products will be allowed.

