10.6.2. Secondary Endpoints

The secondary endpoints of this study are as follows:

- Ad libitum Product Use (Part A)
 - Use the Product Again VAS score
 - Product use behavior (number of units consumed, time spent per unit, number of inhalations per cigarette, duration of gum in mouth)
- Controlled and Uncontrolled Product Use (Part B)
 - Tobacco/Nicotine Withdrawal Questionnaire

- $E_{max_item(\text{controlled})}$: The maximum reduction in VAS score for each item^a between pre-use and post-use (i.e., $VAS_{\text{pre-use}1} - VAS_{\text{post-use}1}$) during the first product use in Part B.
- $E_{max_item(\text{uncontrolled})}$: The maximum reduction in VAS score for each item between pre-use and post-use (i.e., $VAS_{\text{pre-use}2} - VAS_{\text{post-use}2}$) during the second product use in Part B.
- Direct Effects of Product Questionnaire
 - $E_{max_item(\text{controlled})}$: The largest VAS score recorded for the response to each item^b during the first product use in Part B.
 - $E_{max_item(\text{uncontrolled})}$: The largest VAS score recorded for the response to each item during the second product use in Part B.
- Product use behavior (Uncontrolled Use Sessions; number of inhalations, duration of inhalations [per puff], duration of gum in mouth).

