#### PD Parameters

The following subjective effect parameters will be calculated for each subject and treatment:

Questionnaire	PD Parameter	Definition
Tobacco/Nicotine Withdrawal Questionnaire	$E_{max\_item(controlled)}$	The maximum reduction in VAS score for each item during the first product use in Part B
	$E_{max\_item(uncontrolled)}$	The maximum reduction in VAS score for each item during the second product use in Part B
Direct Effects of Product Questionnaire	$E_{max\_item(controlled)}$	The largest VAS score recorded for the response to each item during the first product use in Part B
	$E_{max\_item(uncontrolled)}$	The largest VAS score recorded for the response to each item during the second product use in Part B

The definition of the different item in each questionnaire is detailed in the table below.

Questionnaire	Item	Question
Tobacco/Nicotine Withdrawal Questionnaire	$E_{max\_urge(controlled)}$ $E_{max\_urge(uncontrolled)}$	Urge to smoke
	$E_{max\_anx(controlled)}$ $E_{max\_anx(uncontrolled)}$	Anxious
	$E_{max\_diffct(controlled)}$ $E_{max\_diffct(uncontrolled)}$	Difficulty Concentrating
	$E_{max\_impat(controlled)}$ $E_{max\_impat(uncontrolled)}$	Impatient
	$E_{max\_crav(controlled)}$ $E_{max\_crav(uncontrolled)}$	Craving a Cigarette

Direct Effect of Product	$E_{max\_plst}(\text{controlled})$	Is the product "Pleasant" right now?
	$E_{max\_plst}(\text{uncontrolled})$	
	$E_{max\_stf}(\text{controlled})$	Is the product "Satisfying" right now?
	$E_{max\_stf}(\text{uncontrolled})$	
	$E_{max\_calm}(\text{controlled})$	Is the product making you feel "Calm" right now?
	$E_{max\_calm}(\text{uncontrolled})$	
	$E_{max\_conc}(\text{controlled})$	Is the product helping you "Concentrate" right now?
	$E_{max\_conc}(\text{uncontrolled})$	
	$E_{max\_awake}(\text{controlled})$	Is the product making you feel more "Awake" right now?
	$E_{max\_awake}(\text{uncontrolled})$	
	$E_{max\_sick}(\text{controlled})$	Is the product making you feel "Sick" right now?
	$E_{max\_sick}(\text{uncontrolled})$	
	$E_{max\_hunger}(\text{controlled})$	Is the product reducing your "Hunger" for food right now?
	$E_{max\_hunger}(\text{uncontrolled})$	
	$E_{max\_more}(\text{controlled})$	Would you like "More" of the product right now?
	$E_{max\_more}(\text{uncontrolled})$	

The items  $E_{max\_urge}(\text{controlled})$  and  $E_{max\_plst}(\text{controlled})$  will be the primary endpoints of the study while the remaining items will be secondary endpoints.

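### The uncontrolled-session Direct Effects models adjust for a pre-use rating made 5 to 6 hours after use of the same product, which can shrink the product contrasts

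*SAP*

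**What the plan says.** Protocol 9.4.2 gives one product per Part B day: "On each of the 3 days, subjects will use only one of the 3 study products according to their randomization sequences". Protocol 7.1.2.3 places both sessions on that day: "The Controlled Product Use Session and Uncontrolled Product Use Session will be separated by approximately 6 hours". Both questionnaires have a pre-use rating, and the schedule footnote (Protocol Table 1; attached to both questionnaires in SAP Appendix A) reads "Administered at same time points following the start of the 1st and 2nd product use sessions". On timing, Table 1 adds "Pre-use assessments (not including PK) may be conducted up to 60 minutes prior to product use".

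The two questionnaires yield different endpoints. A Direct Effects E_max in the uncontrolled session is "The largest VAS score recorded for the response to each item during the second product use in Part B" (SAP 9, PD Parameters), with nothing subtracted. A withdrawal E_max is "The maximum reduction in VAS score for each item between pre-use and post-use" (Protocol 10.6.2), and for the uncontrolled session the pre-use score is the one taken before the second use (pre-use2).

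For the analysis, SAP 9 begins its extension to the uncontrolled session and the remaining items with "The same model will be used for" and then gives the covariate rule: "Baseline (pre-use) score will be included as a covariate for all pharmacodynamics measures for which a pre-use score is collected". Protocol 12.4.3.3 carries the same rule. Protocol 12.4.3.2, however, limits the baseline covariate to E_max_urge when it describes the model.

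**The concern.** A covariate is safe to adjust for when the assigned product cannot have influenced it. In the controlled session the pre-use score precedes that day's product. In the uncontrolled session it does not: the subject has already used the product that morning. For an item asking whether the product is pleasant right now, pre-use2 is an earlier same-day rating of the same product. If it already contains part of the difference between own-brand and VLN, holding it constant takes that part out of the estimated contrast.

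The primary objective covers controlled and uncontrolled use. These mixed models are the only planned between-product pharmacodynamic inference for the uncontrolled part; Use the Product Again and product-use behaviour are summarised descriptively. A contrast pulled toward zero would blunt the VLN versus own-brand comparison that the study is meant to make.

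**Working it through.** **Which score enters the model.** The second use starts at about 360 minutes. The pre-use questionnaire may be given up to 60 minutes earlier, so pre-use2 falls between 360 − 60 = 300 and 360 minutes after the start of first use, that is 5 to 6 hours. The SAP's general rule (section 6, Analysis Timepoints) defines baseline as the last value before first dose unless otherwise specified. SAP 9 does specify otherwise by naming the pre-use score. The reduction formula in SAP 9 shows only pre-use1, but Protocol 10.6.2 defines the uncontrolled withdrawal endpoint from pre-use2. Pre-use2 is the natural reading, though the SAP never states it for session 2.

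**Inputs from the documents.** D = 35.21 points is the planned own-brand minus gum difference in controlled-session Pleasant (Protocol 12.2). It is borrowed here for own-brand minus VLN in the uncontrolled session, for which the documents give no figure. The sample-size figures reproduce when the stated SD is read as a within-subject SD in a paired t-test:
- Pleasant: SD of the difference √2 × 31.82 = 45.00; smallest n for 80% power 15, power at the stated 16 is 83.3%.
- Urge: SD of the difference √2 × 28.44 = 40.22; smallest n 53, power at the stated 54 is 81.1%.

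Both rest on the controlled session, so this point does not change them.

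**Assumed inputs (not in the documents).** Residual SD 20 for E_max and 15 for pre-use2; within-subject correlation r between them of 0.3, 0.5 or 0.7; share f of the product difference present in pre-use2 of 0, 0.25 or 0.5.

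**Direct Effects items.** Without the covariate the contrast is D. The product difference in pre-use2 is f × D. With fitted slope b, the adjusted contrast is D − b × f × D = D(1 − b × f). Here b = r × 20/15. The table gives the closed form, with the result of a simulation of the plan's layout (54 subjects, sequences ABC, BCA, CAB, 300 replicates per cell) in parentheses.

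| r | b | f = 0 | f = 0.25 | f = 0.5 |
|---|---|---|---|---|
| 0.3 | 0.40 | 35.2 (35.1) | 31.7 (32.2) | 28.2 (28.4) |
| 0.5 | 0.67 | 35.2 (35.4) | 29.3 (29.2) | 23.5 (23.4) |
| 0.7 | 0.93 | 35.2 (35.2) | 27.0 (27.2) | 18.8 (18.8) |

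The unadjusted simulated estimate stays at about 35 throughout. Taking b down to 0.2, the smallest loss with f above zero is 0.2 × 0.25 = 5%; the largest is 0.933 × 0.5 = 47%. The 20/15 SD ratio matters: with equal SDs b = r, and at f = 0.5 the loss is 15% to 35% instead of 20% to 47%.

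A separate mixed-model simulation (3,000 subjects, own-brand raising pre-use2 by 10 points) gave a VLN minus own-brand contrast in Pleasant of −25.0 without the covariate and −18.3 with it.

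**Withdrawal items.** Write post-use2 = a + b × pre-use2 + product effect. Then E_max = pre-use2 − post-use2 = (1 − b) × pre-use2 − a − product effect. If own-brand lowers pre-use2 by g points and 0 < b < 1, adding the covariate enlarges the own-brand advantage by (1 − b) × g. For g = 10 and b from 0.2 to 0.8 that is 8 down to 2 points. The same simulation design for urge (own-brand lowering pre-use2 by 10) moved VLN minus own-brand from −9.3 to −13.0. The direction is opposite to that for the Direct Effects items.

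**The case against.** **Carry-over at 5 to 6 hours may be negligible.** The items ask about right now, and Protocol 7.2 says the abstinence periods, including the 6-hour gap, are there to minimise residual nicotine effects on baseline. This stands as a limit on size: with f = 0 nothing is lost. It does not make pre-use2 a baseline. The protocol aims to minimise such effects, not to exclude them, and a liking rating need not depend on residual nicotine.

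**The target may be the second use given the state at its start.** Adjusting for that state is then defensible. This is strongest for the withdrawal items, whose endpoint is already measured from pre-use2. It is weaker for the Direct Effects items, whose endpoint is a plain maximum, and neither document states such a target.

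**The covariate is not settled.** Protocol 12.4.3.2 read alone gives the Direct Effects items no covariate. That is correct, and it favours the fix, but Protocol 12.4.3.3 and SAP 9 say the opposite in explicit terms.

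**Pre-use1 could carry product opinion too.** Subjects are unblinded and used all three products in Part A. That is possible, but it would not remove the problem in session 2.

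**The shift will be visible.** Unadjusted E_max summaries and scores by time point are planned for each product and session. They are descriptive, however. The planned sensitivity analysis in completers covers the two controlled-session primary endpoints, so no planned model would show the uncontrolled contrasts without the covariate.

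**Conclusion.** The point holds for the uncontrolled-session Direct Effects items. On the natural reading, the plan adjusts them for a rating made after same-day use of the assigned product, and any product difference in that rating, in the direction of the session maximum, is removed from the contrasts. The loss is b × f: nil if nothing is carried over, and about 5% to 47% over the assumed range. Because b, f, the SDs and the borrowed 35.21 are all assumptions for this setting, the range shows what could happen and is not a prediction.

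A reader might infer three stronger things that the documents do not support:
- That the covariate also removes product effect from the withdrawal items, including urge. Pre-use2 is already inside that endpoint, so the covariate changes the contrast and can enlarge the own-brand advantage.
- That own-brand will in fact be rated higher before the second session. Nothing in the documents shows this.
- That the primary endpoints or the sample size are compromised by this route. Both primary endpoints come from the controlled session, where the pre-use score precedes that day's product.

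**What to change.** In SAP 9 and Protocol 12.4.3.3, limit the covariate rule. Fit the uncontrolled-session Direct Effects E_max models with sequence, period and product as fixed effects and subject within sequence as random, with no pre-use covariate. This agrees with Protocol 12.4.3.2 and removes its conflict with 12.4.3.3 for these models. Keep the pre-use2-adjusted model as a labelled sensitivity analysis.

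For the uncontrolled withdrawal items, state which pre-use score is the session-2 covariate and report the between-product difference in pre-use2, so that readers can see whether adjustment could have moved the contrast.

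The cost is a sentence or two in each document and one term dropped from the model code. All scores are already collected. The downside is possibly wider intervals, to the extent that pre-use2 predicts the later maximum within subjects.
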